The long term goal of the research is to develop non-invasive brain stimulation as an evidence-based tool to facilitate abstinence during the first week after a quit attempt, as this is a robust predictor of 6-month treatment outcomes with traditional pharmacotherapeutic and behavioral interventions. The next step in pursuit of that goal is to systematically and parametrically evaluate the efficacy of two promising TMS treatment strategies (LTP-like stimulation to the mPFC (Aim 1), LTP-like stimulation to the dIPFC (Aim 2)) as tools to change smoking behavior and brain reactivity to smoking cues. These aims will be addressed in serial (Aim 1 Years 1-3, Aim 2 Years 3-5). A randomized, double-blind, sham-controlled design will be used for each aim. In total, 138 smokers will be recruited from the tri-county area surrounding Winston-Salem, NC. Current cigarette smokers seeking to quit smoking and willing to set a quit date will be recruited from the tri-county area using digital and print advertising in diverse media outlets. Following informed consent and screening, participants will be randomized to receive real or sham TMS to the mPFC (Aim 1, Years 1-3) or the dlPFC (Aim 2, Years 3-5) (see Table 1 and TMS Procedures below for more details regarding sham controls and double blinding procedure). During the Treatment Phase, participants will receive 10 sequential days of TMS (with additional behavioral and MRI scanning (see Table 1). Participants will receive TMS at least 3 times a week for a total of 10 TMS sessions. During the follow-up phase, participants will receive 4 maintenance TMS sessions once a week for 4 weeks. During the Follow Up Phase, behavioral assessments will be acquired weekly for the first 4 weeks (see Table 2), and daily EMA will be acquired. Consistent with the CNDS model, the primary hypotheses are that LTP-like stimulation to the mPFC and LTP-like stimulation to the dlPFC will both lead to a decrease in

smoking cue-reactivity in the salience network (neuroimaging outcome), and cigarette value (behavioral outcome) but that directly targeting the value circuit (mPFC) will be more efficacious. Additionally, we will test the hypothesis that individuals with higher discounting rates and cigarette valuation at baseline will respond more to the stimulation strategies compared to those with lower baseline discounting and valuation (Exploratory Aim).

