Study Visit Procedures: At all visits, individuals will provide a urine screen to detect recent use of drugs of abuse and pregnancy, a breath carbon monoxide (CO) sample to detect recent cigarette smoking, and a breath sample to test for recent alcohol use. During the consent visit, visits 1, 6, 10 and follow up visits samples will be collected to determine cotinine (nicotine metabolites) levels in the urine. Samples will be taken from the urine sample provided for the drugs of abuse screen, no additional samples will be required from the participant. At visits 1, 6, 10 and follow up visits (Assessment visits), participants will complete a battery of behavioral assessments following active TMS or sham (see Table 2). MRI scanning (at visits 1 and 10) will occur prior to TMS in order to isolate cumulative, rather than acute, effects of TMS. At all visits participants will be required to provide a CO reading at least 50% of their baseline CO measure to ensure they are at least 6 hours deprived from cigarettes. Cigarette deprivation will be use to increase craving and responding for cigarettes. Short term cigarette deprivation has known amplification effects on the brain response to smoking cues (93, 94). Moreover, we have extensive experience with successfully using this deprivation procedure (33, 41).

Table 2 1. Biochemical and self-report assessment of tobacco use and dependence						
Measure	Time (Min.)	Visits	Description			
Carbon monoxide (CO Level)	1	1-10, and follow-ups	Breath CO provides an accurate measure of recent exposure to CO , including from smoking combustible tobacco products (95). The CO measurement will be used to determine recency of smoking.			
Timeline Follow-Back (TLFB) interview	5	1, 6, 10, and follow-ups	This self-reported tobacco product use interview asks participants to retrospectively estimate the number of tobacco products they've used each day for the past 30 days or since the previous assessment, whichever is fewer (89).			
Fagerström (FTND)	3	1, 6, 10, and follow-ups	This 6-item questionnaire quickly assesses degree of cigarette dependence (96, 97). Test for Cigarette Dependence.			
2. Measures of t	tobacco pr	oduct value an	d sensitivity (**PRIMARY DEPENDENT MEASURES)			

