Questionnaire on Smoking Urges-Brief (QSU)	2	1 - 10 and follow-ups	This 10-item questionnaire assesses cigarette craving . Participants will be asked to rate from 1 (strongly disagree) to 100 (strongly agree) their agreement with several statements (e.g., "I have a desire for a cigarette right now," and "Nothing would be better than smoking a cigarette right now."). Factor analyses support two factors: one that reflects a strong desire and intention to smoke and one that reflects relief from negative affect associated with an urgent desire to smoke (45).			
Hypothetical Purchase Task (**Demand Alpha, Q0) (HPT Cigarettes)	5	1, 6, 10, and follow-ups	The hypothetical purchase task (HPT), a validated measure for cigarette demand, (98, 99) will assess cigarette purchases at various price conditions. Participants will hypothetically purchase quantities of cigarettes to use over a 24-hour period across ascending prices (e.g., \$0, 0.12, \$0.25, \$0.50, \$1.00, and \$2.00 per cigarette). The HPT has been shown to be predictive of treatment outcomes (100).			
3. Cognitive/beha	vioral tasl	k (** PRIMAR	Y DEPENDENT MEASURE)			
Delay- discounting tasks (*discounting rate, \$1K)	5	1, 6, 10, and follow-ups	Participants will be asked to choose between two conditions in which varying amounts and delays to behavioral outcomes (e.g., \$50 now or \$100 later) are presented. We will use magnitudes of \$100 and \$1000 which are the most thoroughly documented among the literature (101). Across consecutive choices, the delay to the larger outcome will be titrated until reaching the participant's indifference delay (i.e., the delay at which s/he equally values both options). This indifference delay indexes individual participants' rates of delay discounting. [61]. Monetary delay discounting has been documented to be predictive to treatment success for smokers (39).			
1. Brain Reactivity to Smoking Cues (**PRIMARY DEPENDENT MEASURE)						

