Behavioral Outcomes: For the treatment phase (10 days of real/sham TBS), the primary behavioral outcomes include Cigarette demand (Q0 and alpha), Craving (QSU Intention, QSU Relief), and Delay Discounting (\$100 and \$1000). For the treatment phase the analysis will be performed using repeated measures ANOVA on change scores from baseline for each visit. The main independent variable in the ANOVA will be time (visits on day 1, 6, 10), group (real or sham) and their interaction. For correlations of observations across visits an AR(1) structure will be considered and compared with other structures such as compound symmetry and a general structure. The primary hypothesis is the interaction. If the interaction effect for an outcome is significant, we will conclude there is statistical evidence of overall treatment effect. If the spaghetti plots suggest trends (e.g., linear, quadratic, or piecewise changes) we will treat time as a continuous variable and fit repeated measures regression models along with group and its interaction with continuous time as independent variables.

Neuroimaging Outcomes: For the treatment phase, primary analysis. Image pre-processing will be conducted with FSL v. 5.0: (FMRIB Analysis Group, Oxford, UK) (108) realignment to the first volume, smoothing with an anisotropic 8-mm Gaussian kernel, high-pass filtering, resampling to 2-mm isotropic voxels, and stereotactic registration to the Montreal Neurological Institute 152-subject average template. Subjects with >3 mm movement (total mean frame displacement across the entire task) will be excluded from analysis.

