
For the follow-up phase: We will test the hypotheses that behavioral change related to Strategy 1 and 2 will be based on an individual's baseline brain cue reactivity data. We will generate Kaplan-Meier curves of behavioral change for the four groups and compare these with cue-reactivity in the MPFC, insula, cingulate (salience network nodes) and striatum using log-rank tests and consider Cox's proportional hazards model to include covariates. Diagnostics will be performed to verify the assumptions such as homoscedasticity and normality. If it is merited, transformations on the outcomes will be considered. Linear contrasts will be utilized to test the hypothesis of equal effects in the two groups at any given time point. Covariates, such as gender and depression that were used to stratify, will be included.

Exploratory Aim: Evaluate baseline frontal striatal connectivity and discounting rate as factors to predict an individual's likelihood of responding to Strategy 1 versus Strategy 2. Finally, will compare the relative efficacy of Strategy 1 versus Strategy 2 on the behavioral change by constructing a computational model. We will test the hypotheses that individuals with a higher ratio of (mPFC-striatal)/(dlPFC-striatal) connectivity will be more likely to have a behavioral change after Strategy 1. Various demographics (e.g. gender, smoking history, socioeconomic status, subclinical depressive symptoms, self-efficacy, & motivation to quit will be evaluated as explanatory variables. This will be achieved by hierarchical linear modeling (HLM v. 7.0, Scientific Software International, Skokie, IL) of the behavioral variables of interest as well as the BOLD signal change in the striatum (caudate) between smoking and image blocks (e.g., CIG vs. NEU) in 'allow' and 'resist' (behavioral change variables nested within treatment (cTBS, iTBS)).

Analytical Plan

Primary data analysis will be done on the Intent to Treat sample (n=138; 69 per Aim: 46 active, 23 sham). Prior to formal statistical analysis, summary statistics for all variables will be obtained and spaghetti plots will be generated. All behavioral outcome measures will be based on standardized composite scores from the literature. We will also use data reduction techniques (such as factor analysis or principle component analysis) to confirm the applicability of the composite scores in our population. Analyses will be performed for each phase separately.

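### The Behavioral Outcomes section and Table 2 do not define the same primary behavioural set, and nothing says which governs

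*Combined protocol and SAP*

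**What the plan says.** Three places in the protocol bear on which behavioural outcomes are primary.

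- **Outcome Measure(s), Behavioral Outcomes.** For the treatment phase, "the primary behavioral outcomes include Cigarette demand (Q0 and alpha), Craving (QSU Intention, QSU Relief), and Delay Discounting", and the sentence goes on to give discounting at both $100 and $1000. That makes six variables: Q0, alpha, QSU Intention, QSU Relief, $100 discounting and $1000 discounting. The same paragraph says that a significant group-by-time interaction for an outcome is evidence of an overall treatment effect.
- **Table 2.** The section on tobacco product value and sensitivity is headed as primary, in the plural, and contains two rows. The purchase-task row carries a double asterisk beside Demand Alpha and Q0. The row "Questionnaire on Smoking Urges-Brief (QSU") carries no mark. The cognitive/behavioural section is also headed as primary, in the singular. Its row reads "discounting tasks (*discounting rate, \$1K"), with one asterisk. The description of that row adds "We will use magnitudes of \$100 and \$1000", so both magnitudes are collected but only one is named in the label.
- **Design.** The primary hypotheses concern a decrease in "smoking cue-reactivity in the salience network (neuroimaging outcome), and cigarette value (behavioral outcome").

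The Sample Size section refers to several primary outcome measures without listing them.

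**The concern.** With a rule that works outcome by outcome, membership of the primary list can decide whether the trial is called positive. A result on $100 discounting alone is a primary success under Behavioral Outcomes but is not marked in Table 2. A result on craving alone is a success under Behavioral Outcomes, and under Table 2 only if the headings rather than the row marks define primary status.

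This question comes before multiplicity adjustment, because an adjustment needs a fixed family. It also has a practical edge. Plans for Interim Analysis of Efficacy Data provides for analyses at each 20% of recruitment, with unblinding codes for completed participants given to the principal investigator. If the list stays open, it could be settled after group results have been seen.

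**Working it through.** **Step 1: the lists side by side.**

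| Reading | Variables | Number |
|---|---|---|
| Behavioral Outcomes | Q0, alpha, QSU Intention, QSU Relief, $100, $1000 | 6 |
| Table 2 by section headings | Q0, alpha, QSU Intention, QSU Relief, $1000 | 5 |
| Table 2 by row marks | Q0, alpha, $1000 | 3 |
| Cigarette value (Design), taken as demand | Q0, alpha | 2 |

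The lists are nested: each shorter list is contained in the list of six.

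**Step 2: how often the readings disagree under no effect.** Assumptions: two-sided tests at an unadjusted 5% (the protocol does not state sidedness), normal test statistics, and equal correlation r between every pair of outcomes. The documents give no between-outcome correlations, so r = 0.5 is an assumption, shown with a range of 0 to 0.9.

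With φ and Φ the standard normal density and distribution function, the chance that none of k outcomes is significant is

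N(k) = ∫ φ(u) [Φ((1.96 − √r·u)/√(1−r)) − Φ((−1.96 − √r·u)/√(1−r))]^k du,

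which is 0.95^k at r = 0. The chance of at least one significant outcome is 1 − N(k):

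| k | r = 0 | r = 0.5 | r = 0.9 |
|---|---|---|---|
| 2 | 9.75% | 9.1% | 7.0% |
| 3 | 14.3% | 12.5% | 8.4% |
| 5 | 22.6% | 18.3% | 10.2% |
| 6 | 26.5% | 20.7% | 10.8% |

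Because the lists are nested, the chance that the six-outcome list succeeds while a shorter list of k fails is N(k) − N(6), taken before rounding:

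| Six outcomes against | r = 0 | r = 0.5 | r = 0.9 |
|---|---|---|---|
| Table 2 by headings (5) | 3.9% | 2.4% | 0.7% |
| Table 2 by marks (3) | 12.2% | 8.2% | 2.5% |
| Demand only (2) | 16.7% | 11.6% | 3.8% |

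These figures are per Aim and cover the behavioural outcomes at one analysis.

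**Step 3: the plan's power figure, and what adjustment costs.** The Sample Size section states 80% power at a 5% error rate for d = 0.8 with 108 usable data sets. That is 108/2 = 54 per Aim, or 36 active and 18 sham at 2:1. For a simple two-group comparison, 0.8/√(1/36 + 1/18) = 0.8/0.2887 = 2.771, and Φ(2.771 − 1.960) = 79.1%. This reproduces the stated figure approximately for one unadjusted outcome. The repeated-measures calculation itself cannot be rerun, because its AR(1) correlations are not given.

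With a Bonferroni split of 5%:

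- 2 outcomes: Φ(2.771 − 2.241) = 70%
- 3 outcomes: Φ(2.771 − 2.394) = 65%
- 5 outcomes: Φ(2.771 − 2.576) = 58%
- 6 outcomes: Φ(2.771 − 2.638) = 55%

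Holm's procedure is never less powerful than Bonferroni, so these are floors for per-outcome power under this approximation.

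**The case against.** The strongest reply is that Behavioral Outcomes is the dedicated outcome section, lists its primaries explicitly, and would ordinarily be taken to govern. The Design sentence is then a summary of hypotheses. Much of this stands. A reader might infer from Design that cigarette value is the only primary behavioural outcome, so that three rival definitions exist. The text does not support that: it never says only, and the Sample Size section speaks of several primary measures. The demand-only row in the working is therefore an outer bound.

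Table 2 may also be close to the outcome section. QSU sits under a heading labelled primary, and if the heading governs, the two places differ only on $100 discounting. The single asterisk on discounting, against two on demand, has no legend and may be a typing or text-extraction slip. It cannot bear weight. What remains is that the row names $1K although both magnitudes are collected.

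The decision rule could be meant outcome by outcome, with overall referring to visits. The list would then still decide which results may be reported as primary.

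Two further inferences should be resisted. One is to read the 20.7% chance of any false positive among six outcomes as the size of this discrepancy. That figure comes from the unadjusted any-outcome rule, and the cost of the conflicting lists is the disagreement rate. The other is to treat the Analytical Plan's sentence, "All behavioral outcome measures will be based on standardized composite scores from the literature", as further conflict. It concerns scoring and does not bear on which outcomes are primary.

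**Conclusion.** The discrepancy is real and should be reconciled. Its firm core is that $100 discounting is primary in Behavioral Outcomes and unmarked in Table 2, that the status of the QSU factors in Table 2 is unclear, and that no sentence says which list governs.

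The size depends on the reading. On the most charitable one (Table 2 by its headings), the disagreement under no effect is small, at 0.7% to 3.9% of trials. It rises to between 2.5% and 12.2% if only marked variables count. These ranges rest on the assumed correlations, two-sided unadjusted tests and no true effect. If an effect exists on craving or $100 discounting only, the frequency of disagreement would differ, and it has not been computed here.

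**What to change.** Before any further unblinded look under the interim analysis plan:

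1. State one primary behavioural list, make Design, Table 2 and Behavioral Outcomes match it, and say that it governs.
2. Use $1000 as the primary discounting magnitude, as Table 2 already names it, and make $100 a sensitivity analysis.
3. State explicitly whether QSU Intention and QSU Relief are primary, and explain or remove the asterisks.
4. Replace the any-outcome rule with one that holds the 5% error over the chosen list, for example Holm. If the sponsor prefers, name a single primary variable instead.

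Which outcomes belong on the list is the sponsor's choice, and keeping the list in Behavioral Outcomes apart from $100 discounting would be a legitimate answer.

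The change is to wording only, and every measure is still collected. There are two costs. Outcomes left off the list cannot carry a primary claim alone. Adjustment over several outcomes also takes per-outcome power below the stated 80%, to a floor of about 58% with five outcomes or 65% with three, on the approximation above.

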TMS ACTIVE SHAM system and strategies to promote rigor of the blind: The MagVenture MagPro system has an integrated active sham that used two surface electrodes placed on the scalp to mimic the sensation of active TMS. The coil is visually identical on both sides, but only one side will direct an electric field on the participants head. At each TMS visit, the coordinator will place 2 surface electrodes on the scalp near the TMS stimulation site. Once the electrodes are in place and the TMS coil is in position, the coordinator enters a 6 digit number assigned to that participant into the MagPro capacitor. Each number is coded to be either active or sham TMS, but the classification is unknown to the coordinator or the participant. The capacitor can sense whether the TMS coil is positioned in a direction wherein the active or the sham side is facing the participant's head. The capacitor will instruct the coordinator that is either "Ready" or to "Flip Coil" based upon the participants group assignment. This enables both the participant and the coordinator to be blind.

For the initial TMS visit, during the motor threshold procedure, the active side is always down in order to determine an appropriate dose To ensure that the coordinator (who both finds the motor threshold and then delivers the treatment) does not learn the relationship, on Visit 1 after the motor threshold procedure is done, the coordinator will leave the room and a second individual will unplug the coil, flip it 1 or more times, and leave the room. The coordinator will return to the room, plug it in, place the TMS coil in the proper position, and commence the treatment.

Further strategies to promote blinding: The TMS coil will be visually inspected by the PI or lab manager on a regular basis to be sure that no marks have occurred on the surface of the coil. If marks have occurred they will be either washed off or covered in a manner that is symmetrical to both sides of the coil. Additionally all staff will be trained on the importance of blinding when they join the laboratory and encouraged to contact the lab manager or the PI if they ever feel they may have "figured out" the blind. A questionnaire will be given to the participants to evaluate their opinion on whether they received active or sham, their level of confidence (Likert scale 1-10), and their rationale (text entry).

Outcome Measure(s)

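### The coil-flip step does not randomise the final side from a known start, so a one-flip habit would let the machine's message disclose the arm; coordinator blinding is not formally assessed

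*Combined protocol and SAP*

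**What the plan says.** The procedure is in the combined protocol and SAP, in the paragraphs on the active sham system and the rigor of the blind.

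- **Starting side.** At the first TMS visit, "during the motor threshold procedure, the active side is always down in order to determine an appropriate dose".
- **Who knows it.** One person does both steps. The safeguard exists so that "the coordinator (who both finds the motor threshold and then delivers the treatment) does not learn the relationship".
- **The safeguard.** Once the threshold has been found at Visit 1, the coordinator steps out. In that interval, "a second individual will unplug the coil, flip it 1 or more times, and leave the room". Afterwards it is again the coordinator who reconnects and positions the coil and treats. The text gives no rule for the number of flips and no random choice between odd and even.
- **The message.** The two sides look the same, but the device senses which one faces the head and shows 'Ready' or 'Flip Coil' according to the assigned arm.
- **Checking the blind.** "A questionnaire will be given to the participants to evaluate their opinion on whether they received active or sham", with a confidence rating and a reason. Table 2 schedules the participants' confidence form at Visits 1, 6 and 10. Staff are trained on blinding and encouraged to tell the lab manager or principal investigator if they think they have worked it out. No coordinator form, schedule or analysis is described.
- **Allocation.** The TMS treatment section gives 2:1 active to sham. The Sample Size section gives 46 active and 23 sham per Aim.

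**The concern.** The step is meant to break the link between a side the coordinator knows and the message the coordinator then sees. It does so only if the side left down is unpredictable. An odd number of flips leaves the sham side down and an even number leaves the active side down. If the second person habitually flips once, 'Ready' means sham and 'Flip Coil' means active. That habit complies fully with the written instruction.

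At stake is the operator half of a trial described as double-blind. The primary behavioural outcomes (cigarette demand, craving, delay discounting) are participants' own ratings or choices, collected after TMS at the assessment visits. Booklet material is also discussed at each TMS visit. A coordinator who inferred the arm at Visit 1 could carry that knowledge into later contact with the participant. The planned blinding form would not directly show it, because only participants complete it.

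**Working it through.** The protocol states no figure for coordinator blinding, so there is none to reproduce. The arm sizes are consistent with the allocation ratio: 2 × (46 + 23) = 138, and 46/69 = 0.667.

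**Inputs**
- Prior probability of active: 2/3 (TMS treatment section; Sample Size section).
- Starting side: active down, known to the coordinator (active sham section).
- q, the probability that the number of flips is odd: not in the documents. It is an assumption, shown from 0.5 to 1.
- Further assumptions: the coordinator keeps the coil the way up it was found, cannot otherwise tell the sides apart, and knows roughly what the second person tends to do.

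**Formulas.** 'Ready' appears when the side down matches the arm. That means active with an even count, or sham with an odd count.

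- P(active | 'Ready') = (2/3)(1−q) / [(2/3)(1−q) + (1/3)q]
- P(active | 'Flip Coil') = (2/3)q / [(2/3)q + (1/3)(1−q)]
- Best-guess accuracy = max[(2/3)(1−q), (1/3)q] + max[(2/3)q, (1/3)(1−q)]

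**Worked example, q = 0.8**
- 'Ready': 0.1333 / (0.1333 + 0.2667) = 0.333
- 'Flip Coil': 0.5333 / (0.5333 + 0.0667) = 0.889
- Accuracy: 0.2667 + 0.5333 = 0.80

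| q | P(active) after 'Ready' | P(active) after 'Flip Coil' | Best-guess accuracy |
|---|---|---|---|
| 0.5 | 0.667 | 0.667 | 66.7% |
| 0.6 | 0.571 | 0.750 | 66.7% |
| 0.667 | 0.500 | 0.800 | 66.7% |
| 0.8 | 0.333 | 0.889 | 80% |
| 0.9 | 0.182 | 0.947 | 90% |
| 1 | 0 | 1 | 100% |

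Over this range, accuracy stays at the 66.7% obtained by always guessing active until q exceeds 2/3, and equals q after that. Between 0.5 and 2/3 the message shifts the probabilities without improving the best guess. A fixed even habit is equally disclosing in the other direction: at q = 0 the probabilities are 1 and 0.

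**Which feature of the rule matters**
- 1 or 2 flips with equal chance: q = 0.5, no leak.
- 0 or 1 flip with equal chance: q = 0.5, no leak.
- 1, 2 or 3 flips with equal chance: q = 2/3, giving 0.50 / 0.80.
- 0, 1 or 2 flips with equal chance: q = 1/3, giving 0.80 / 0.50.

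The balance of odd and even decides the leak, not the minimum count. The minimum of one affects only the likely direction. If larger counts are never more likely than smaller ones, then P(1) ≥ P(2), P(3) ≥ P(4) and so on, so q is at least 0.5.

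**The case against.** A reader might infer that the fault is the exclusion of zero flips. It is not. Two flips leave the coil as zero would, the wording allows two, and adding zero without a random rule can itself create a leak.

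A reader might also infer that the message necessarily reveals the arm. The documents do not support that. The coordinator is out of the room and does not see the count, the sides look identical, and the coil is unplugged and then repositioned by hand. Inference requires a predictable habit and a coordinator who keeps track of orientation. The value of q is unknown, and a moderate imbalance (q up to 2/3) gives no better best guess than always saying active.

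Two further extensions go beyond the text. The protocol does not say that one coordinator treats a participant at every session, or who leads the booklet discussion. Nor would a broken operator blind necessarily go unnoticed, since staff may report it and participants give a free-text reason for their guess. Not every outcome is open to the same influence either: cue reactivity on fMRI is also a primary measure, and breath CO and urine cotinine are collected.

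Finally, the TMS treatment section says blinding follows prior publications and that a standard operating procedure will be published. A flip rule may exist there, outside the documents available.

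These points limit the size and certainty of the problem. They do not remove it: the rule as written can be followed exactly while disclosing every assignment. Voluntary self-report cannot show that the operator blind held.

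**Conclusion.** The point holds as a weakness in the written safeguard, not as demonstrated unblinding. The final coil side is left to the second person's discretion from a start the coordinator knows. The consequence ranges from nothing at q = 0.5 to full disclosure at q = 1, with 80% best-guess accuracy at q = 0.8 against a 66.7% prior. These figures rest on the 2:1 ratio, which the protocol states. They also rest on q, on the coordinator keeping the coil as found, and on some knowledge of the second person's habit, none of which the protocol states. Separately, coordinator blinding has no formal assessment; the only route is voluntary reporting. The change is worth making because it removes the dependence on q at almost no cost.

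**What to change.** Replace the discretionary flip count with a final orientation taken from a concealed, pre-generated random list. The list should give each side equal probability and be independent of the treatment allocation. The second person sets the coil accordingly, out of the coordinator's view. One or two flips with equal chance would achieve this within the present minimum of one. The probability of active is then 0.667 after either message, equal to the prior, so the message tells the coordinator nothing.

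Optionally, record the coordinator's guess and confidence on the existing form at Visits 1, 6 and 10, alongside the participant's. If a standard operating procedure already fixes the flip rule, state it in the protocol.

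The cost is a change of wording, a random list, negligible time and, if adopted, one form field. The second person is already part of the procedure.
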